Appendix 10: Appointment Reminder Card

Appendix 11: Completion Certificateions" Leaflet for
Mailing

TCU
1920-347
Approved on 2-8-2023
Expires on 1-24-2024

Summary

The purpose of the Substance Use and Health Risk Intervention (SUHRI) project is to adapt and test an integrated health risk-reduction and motivational enhancement intervention (a cloud-based app) for Juvenile Justice (JJ) youth that will ultimately be (after full testing through a subsequent large-scale RCT) a sustainable intervention implemented within a JJ supervision/case management context to teach and facilitate positive, prosocial, and expected behaviors. The intervention will use interactive graphical approaches to encourage introspection and problem identification, enhance self-regulation, improve analytical problem-solving skills, and promote healthy behaviors in two inter-related target areas: substance use and risky sex practices. App sessions will be self-directed (require minimal instruction/interaction assistance), and also include a service referral piece whereby youth are provided with additional resources for seeking services related to risky health behaviors and substance use.

This research will be carried out in two pilots: (1) Intervention Adaptation and Feasibility and (2) Protocol Feasibility. The specific aims of the project are to (a) examine intervention feasibility and acceptability (Pilot 1), (b) *test the feasibility of the study protocol (adherence, subject retention, instrumentation) with JJ-involved youth (Pilot 2).*

During Pilot 1, intervention content will be adapted from existing evidence-based interventions so that it is developmentally appropriate for the target population and suitable for a web-based format. During Pilot 2, a test of the intervention will yield data on intervention feasibility, acceptability, and impact on youth outcomes. Proximal outcomes include improvements in change mechanisms (e.g., problem recognition, decision making, intention to reduce personal risk) and service initiation (SU or STI-related services). Distal outcomes include reduction in risky behaviors, including substance use (self-report and urinalysis) and sexual health risk (self-reported risky sex practices). Successful completion of the aims will result in an intervention that is appropriate and feasible for use with JJ-involved youth.

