To request corroborating data from the local JJ department as well as the Texas Department of Juvenile Justice (TJJD), the research team will request that the TCJS research director provide the TJJD-based identification number (PID) for consenting participants as well as demographic, substance screening and assessment, and relevant service attendance information. These data will be shared via a spreadsheet available to the director of research and the research team via Box.com – a secure file-sharing platform. The research team will provide the PID numbers along with headquarters county ID to the TJJD data team via spreadsheet in a Box folder in return for state-level data specific to the youth's substance use screening and assessments as well as offense, background, and service-seeking data. The TJJD research proposal submitted in September 2020 can be found in Appendix 9. be found in Appendix 9.

Intervention

The youth will receive 4 sessions of the interactive, cloud-based intervention administered via a tablet we give them. Each session of the intervention will focus on one of topics associated with drug use and risky sex practices. The final session will include an integrated module ensuring that youth process through a scenario that examines how drug use and risky sex behaviors are related. The youth will complete the final WORK-IT scenario within the app with processing questions (see Appendix 5.7) to work through this integrated scenario and also a quiz-like activity on Kahoot to learn more about local resources for substance use and sexual health.

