Risks are minimal and include potential risks to breach of confidentiality. No physical risks are involved in participation. Minimal risk of emotional discomfort may exist. Because youth will be asked about substance use and risky sex behaviors, minimal risk of emotional discomfort may exist. Exposure to some content within the intervention could trigger memories of events if the individual has experienced something similar. TCU RAs will be trained on identifying symptoms of trauma, handling information disclosed by the youth or caregiver, and will follow specific procedures required by each department for reporting abuse or trauma to health personnel. Steps will be taken to minimize risks introduced by meeting virtually (e.g., using meeting specific links, HIPAA-comparable security settings for virtual meeting platforms, and passwords to join, and emphasizing the need for maintaining confidentiality). Any reports or papers produced with data, will maintain respondent confidentiality; no identifiable individual responses will be disclosed.

SUHRI DATA AND SAFETY MONITORING PLAN

Our Data and Safety Monitoring Plan (DSMP) will be consistent with plans and procedures we have used in our other federally-funded research projects. These include installation of an 800 (toll free) number in the US for research sites to use for reporting adverse events (AEs) to the PI, Co-Is, and research team. The PI will serve as liaison with our university IRB and will monitor and report problems and AEs as directed. Specific plans and reporting formats will be developed and reviewed and approved by the IRB prior to the onset of any research involving the proposed pilot studies. Reporting forms will be developed and participating staff will be trained to identify and report problems and AEs. The agenda for the weekly data management team meetings also will include problem and adverse events reports, and all reports will be immediately forwarded to the PI. The PI will assume overall responsibility for assuring the safety of study participants and will assure that the TCU IRB is informed of all safety issues.

Definitions of Adverse and Serious Adverse Events

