The proposed studies will follow established procedures based on our previous NIDA studies outlining Common Adverse Events (AEs) and Serious Adverse Events (SAEs) for substance abuse research. Adverse events are defined as any event or outcome that has resulted in harm to the participant, has affected the participant detrimentally, has worsened as a result of participation in the study, or has resulted in increased risk to the participant or others whether or not the risk actually results in harm.

SUHRI DATA AND SAFETY MONITORING PLAN

Our Data and Safety Monitoring Plan (DSMP) will be consistent with plans and procedures we have used in our other federally-funded research projects. These include installation of an 800 (toll free) number in the US for research sites to use for reporting adverse events (AEs) to the PI, Co-Is, and research team. The PI will serve as liaison with our university IRB and will monitor and report problems and AEs as directed. Specific plans and reporting formats will be developed and reviewed and approved by the IRB prior to the onset of any research involving the proposed pilot studies. Reporting forms will be developed and participating staff will be trained to identify and report problems and AEs. The agenda for the weekly data management team meetings also will include problem and adverse events reports, and all reports will be immediately forwarded to the PI. The PI will assume overall responsibility for assuring the safety of study participants and will assure that the TCU IRB is informed of all safety issues.

Definitions of Adverse and Serious Adverse Events

The proposed studies will follow established procedures based on our previous NIDA studies outlining Common Adverse Events (AEs) and Serious Adverse Events (SAEs) for substance abuse research. Adverse events are defined as any event or outcome that has resulted in harm to the participant, has affected the participant detrimentally, has worsened as a result of participation in the study, or has resulted in increased risk to the participant or others whether or not the risk actually results in harm.

Specific Adverse Events (as observed or reported by participants or staff) include:

Violation of confidentiality (e.g., release of participant data to a non-authorized 3rd party)

Institutionalization in residential treatment or substance use rehabilitation

Probation revocation, re-arrest, reincarceration (e.g., jail, prison, juvenile detention)

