Training of staff will include information on the definitions of SAEs and AEs and reporting procedures. SAEs will be identified by a proactive system of “incident” reports filed in relation to providing interventions or participating in the research procedures. These events will be reviewed by the PI and graded for their severity and attribution to the intervention, and ALL events will be reported in writing to the local IRB within 3 business days. Also, in accordance with local reporting requirements, all AEs occurring during the course of the study will be collected, documented, and reported by the investigators to the IRB at the time of their annual continuing reviews. The PI will prepare a summary report of all Adverse Events to be submitted to the IRB. The analysis of all adverse events accumulated-to-date will include a listing of all AEs.

Incident Reporting and Procedures

Any SAE, whether or not related to study intervention, will be reported to the PI within 24 hours of detection. Within 3 business days, the PI will submit a completed SAE report to the IRB. Written reports of adverse experiences will follow statutory regulations.

In the event that a subject either withdraws from the study or the investigators decide to discontinue a subject due to an SAE, the subject will be monitored by PI via ongoing status assessment until (1) a resolution is reached (e.g., the problem requiring hospitalization has resolved or stabilized with no further changes expected); (2) the SAE is determined to be clearly unrelated to the study intervention; or (3) the SAE results in death. Outcome of SAEs will be reported to the IRB in quarterly reports. A summary of the SAEs that occurred during the previous year will be included in the annual progress report to NIDA.

The DSM report, to be submitted with the annual progress report, will include information organized into the following sections: study description, sociodemographic characteristics of the accumulated participants at baseline (pre-intervention assessment), data on the status of study participants, quality assurance issues, regulatory issues, data on AEs and SAEs, and efficacy.

Approach for Reviewing Problems

Each AE will be classified by the PIs as serious or non-serious and appropriate reporting procedures will be followed as stated above. The PIs will classify each SAE according to the following attribution of risk categories:

Definite: SAE is clearly related to the intervention

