Probable: SAE is likely related to the intervention Possible:
SAE may be related to the intervention Unlikely: SAE is
doubtfully related to the intervention Unrelated: SAE is
clearly not related to the intervention

Participants' descriptions of adverse events (incident reports) will be grouped in a reasonable way, counted, and compared by study groups. A designation of "more-common" will be given to events occurring at an incidence of at least 5% in participants assigned to an intervention group, and for which the incidence is at least twice that observed in a comparison group. Staff will be trained to carefully observe participants' reactions to the study protocol and to take appropriate action including support, discontinuance, or referral to additional counseling services, if necessary. Based on previous experience and the current use of these TCU materials with other IRB research projects we have found that such occurrences are rare.

Reporting Timeline

SAEs will be reported to the PI within 24 hours of detection. Within 3 business days, the PI will send a full report on the SAE, including the action taken with regard to continued study participation to the IRB. Non-serious AEs or adverse effects that lead to subject removal from the protocol will be reported to the IRB within 7 business days. The PI will maintain a record of the SAEs, which can be provided to the IRB electronically. The outcome of SAEs also will be reported to NIDA in annual reports. A summary of the SAEs and AEs that occurred during the previous year will be included in the annual progress report to NIDA.

17. Potential Benefits:

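### The adverse-event rule needs a comparison group, and the dropout and abstinence tests need groups or a reference, but Pilot 2 is described as a single group

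*Combined protocol and SAP*

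**What the plan says.** **Design.** Section 12 plans to recruit about 60 youth and does not divide them. Section 15 gives one pathway: consent and assent, baseline assessment, tablet, four sessions, follow-up assessments. Under its Intervention heading it says "The youth will receive 4 sessions of the interactive, cloud-based intervention administered via a tablet we give them". The Summary says the app would be ready for sustained use only "after full testing through a subsequent large-scale RCT", and Section 20 also treats the randomised trial as future work. The protocol text available describes no allocation step, control condition, wait-list or external comparator.

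**Safety rule.** In Section 16, the part of the Data and Safety Monitoring Plan headed Approach for Reviewing Problems says that incident reports will be grouped, "counted, and compared by study groups". The 'more-common' label requires an incidence of at least 5% in "participants assigned to an intervention group", and it applies only to events "for which the incidence is at least twice that observed in a comparison group". The same plan lists this category as an adverse event: "Probation revocation, re-arrest, reincarceration (e.g., jail, prison, juvenile detention".

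**Analysis.** Section 20 compares abstinence at each follow-up by chi-square and assesses intervention dropout by log-rank. It names no groups and no reference for either. It also says that multiple imputation gives unbiased estimates of a treatment effect, without defining the contrast.

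**The concern.** A rule that divides by a comparison-group incidence cannot be completed when there is no such group. The gap falls where a comparator would be most useful. Youth under supervision can be re-arrested or have probation revoked without any intervention, so a raw count of these events does not show whether the intervention played a part. The written rule appears to answer that question, but in this design it does not.

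Retention is a stated aim of Pilot 2 (Summary), yet the only method Section 20 names for intervention dropout is a test between unspecified groups. It does not produce the figure that a reader of a feasibility study wants, which is the proportion who stayed and how precisely it is known. Section 20 also sends effect sizes forward to size the later trial without saying which effects. A change within participants is not a difference between arms.

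**Working it through.** The plan gives no figure to reproduce for this point: no alpha, power, event rate, allocation ratio or dropout rate. The check sets the stated rules against the described design and then works out what one group can report.

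**Inputs from the protocol:** n of about 60 (Section 12), and the limits of 5% and two-fold (Section 16). The event counts below are illustrations, not protocol figures.

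**1. The two conditions of the label, with one group of 60.**
- The 5% condition: 0.05 × 60 = 3 youth. Two of 60 is 2/60 = 3.3% and fails, so an event in 0, 1 or 2 youth is not 'more-common', whatever a comparator might have shown.
- The two-fold condition: intervention incidence ≥ 2 × comparison incidence. The right-hand side is undefined without a comparison group.
- Both conditions must hold. From 3 of 60 upward the first is met and the second has no value. At 12 of 60 re-arrested (20%) the rule gives neither yes nor no.

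**2. What one group can report for each event type.** The exact (Clopper-Pearson) 95% interval for x events in n has lower limit B(0.025; x, n − x + 1) and upper limit B(0.975; x + 1, n − x), where B is the beta quantile. For x = 0 the lower limit is 0 and the upper limit is 1 − 0.025^(1/60) = 6.0%.

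| Events | Incidence | Exact 95% CI |
|---|---|---|
| 0 of 60 | 0% | 0 to 6.0% |
| 3 of 60 | 5% | 1.0 to 13.9% |
| 12 of 60 | 20% | 10.8 to 32.3% |

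**3. Dropout.** The usual log-rank statistic sums observed minus expected events in one group, with expectation taken from the pooled risk set. With a single group, observed equals expected at every event time and the sum is zero. A one-sample version needs a reference curve, and Section 20 gives none. A direct estimate is available: if 48 of 60 completed, retention is 48/60 = 80%, exact 95% CI 67.7 to 89.2%.

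**4. Abstinence.** The sentence reads most naturally as a between-group comparison at each follow-up, but no groups are named. The exploratory comparison by sex stands in a separate sentence, with its own list of tests, and is not tied to this one. If the test were instead run across visits in the same youth, the observations would be paired and an independent-samples chi-square would not fit.

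**5. Timing of any change from baseline.** Within Section 15, Procedures schedules a 1-month assessment following the last session and a further one 3 months after the intervention. The Assessment heading counts 1 and 3 months from baseline. The sessions span about 1 month. Measured from the first session, the first reading puts the assessments at about 1 + 1 = 2 and 1 + 3 = 4 months; the second puts them at 1 and 3 months, the earlier one at about the end of the sessions. Change from baseline is not well defined until these passages agree.

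**The case against.** The strongest reply is that little depends on the label. The safety plan attaches no action to it. The plan promises that "The analysis of all adverse events accumulated-to-date will include a listing of all AEs", and serious events go to the IRB on fixed timelines with attribution by the investigators. The plan also "will be consistent with plans and procedures we have used in our other federally-funded research projects", so the rule may be wording carried over from a study with arms. All of this stands, and it limits the severity. It does not make the rule usable, and carried-over text in an approved plan still needs correcting.

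Four stronger readings are tempting, and the documents do not support them.

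- *No event can be assessed under the rule.* This goes too far, because events below 5% fail the first condition without a comparator.
- *A log-rank test is impossible in one cohort.* A one-sample form against a reference curve exists. The supportable point is that Section 20 names neither groups nor a reference.
- *The mention of a treatment effect shows that a second arm is required.* The phrase sits in a general description of what imputation provides and could mean change from baseline. What can be said is that its contrast is undefined.
- *Retention will go unsummarised.* Section 20 has implementation feasibility measures recorded, summarised and reviewed monthly, which would naturally cover retention. What is missing is a stated final whole-cohort estimate with its precision.

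It is also fair to say that chi-square and log-rank tests are valid for independent subgroups such as sex. The plan then has to say that those are the groups.

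**Conclusion.** The point holds and should be fixed, with limited impact. On the design as described, the 'more-common' rule cannot classify any event seen in 3 or more of 60 youth, and the dropout and abstinence tests give no whole-cohort result as written. This is more than missing detail, because a stated rule cannot be carried out in the stated design.

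The conclusion rests on the protocol text available, which contains no comparison group, and on enrolment of about 60; the count that meets the 5% condition is 0.05 × n and moves with enrolment. A reader might infer that safety oversight is compromised or that an efficacy conclusion is at risk. Neither follows: event listing and serious-event reporting run without the label, and efficacy is exploratory. No numerical error in the plan is alleged.

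**What to change.** First, state whether Pilot 2 is single-arm. If it is not, describe the comparison group and how youth are assigned to it, and reconcile Section 15 with the safety plan in Section 16.

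If it is single-arm:

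1. Replace the two-fold 'more-common' label with the incidence and exact 95% confidence interval for each event type, alongside the listing already planned.
2. Report whole-cohort intervention dropout as a Kaplan-Meier curve or as the percentage completing each of the four sessions, with 95% intervals. Report abstinence at each follow-up as a proportion with its 95% interval. Keep chi-square and log-rank tests only for named subgroups such as sex.
3. Define the contrast meant by treatment effect. Describe any change from baseline as within-participant change and analyse it with a paired or repeated-measures method. Do not carry it into the later trial's sample size as a between-arm effect without a stated control-arm assumption.
4. Reconcile the post-intervention and post-baseline assessment timings in Section 15 before defining change.

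The cost is rewording in Section 20, one paragraph of the safety plan and the timing text in Section 15, with no added data or participants. The downside is that results are openly within-group only, and sizing of the later trial rests on a control-arm assumption that this pilot cannot estimate.

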To ensure fidelity to the study protocol and to avoid any perceived coercion by JJ staff, TCU Institute of Behavioral Research (TCU/IBR) RAs will oversee intervention administration, including voluntary study enrollment and withdrawal if requested. Following our NIDA-funded JJ- TRIALS study protocol, NO participant information (youth participation, youth assessment responses, choices/responses selected during the intervention, completion of sessions) will be shared with JJ staff; only aggregate information will be shared with JJ leadership.

11. Location:

All intervention and assessments sessions will take place either online using a platform such as Zoom, in-person at a Tarrant County Juvenile Services office or another public place, or via a tablet hand-off in an agreed upon public place. All TCU rules and regulations regarding COVID-19

protocols will be followed for in-person interactions including masking, hand-washing/sanitizing, social distancing when able, and sanitizing of all equipment.

12. Subject Population:

Participants will include juvenile justice-involved youth on probation within at least 1 local juvenile probation department (Tarrant County, currently). The Tarrant County Board (TCJS) has granted preliminary approval to submit appropriate requests to TJJD to move forward with planning this study.

We expect to recruit approximately 60 youth who range in age from 14 to 18 years old.

Inclusion Criteria: Youth ages 14-18 on community supervision are eligible if they have 1 or more indicator(s) of substance use, are English-speaking, and have no indication of current suicide risk or severe cognitive impairment/thought disorders. Youth's parent/legal guardian may be Spanish-speaking. Upon approval of the parental consent document, it will be translated into Spanish and submitted to the IRB for approval.

Exclusion criteria: Youth who are on TJJD (state) supervision rather than county supervision are not eligible to participate. In addition, youth who are currently suicidal, homicidal, or otherwise severely impaired (e.g., active psychotic symptoms) such as severe cognitive impairment or thought disorders are not eligible. Youth younger than 14 and youth 19 or older are likewise not eligible.

13. Recruitment Procedure:

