Specific Serious Adverse Events (as reported by the partner JJ agency or youth participants) include:

Drug overdose

Death

Serious injury

Life-threatening experience

Suicide attempt

Hospitalization

Impairment due to a persistent or significant disability or capacity

Unexpected events are defined as any event or outcome that was not described as a risk of participation in the research or, even though described as a risk, which has occurred with unexpected severity or frequency. These SAEs will be monitored in interim analyses and will be systematically assessed as part of the post-intervention assessment. Although the enrolled participants are not considered to be at elevated risk for suicide (due to exclusion criteria), our collaborating JJ agency screens, identifies, and monitors mental health and suicide risk on an on-going basis and adheres to all local, state and federal policies regarding required reporting and intervention procedures. Specifically, all departments within the state of Texas are required to administer the Massachusetts Youth Screening Instrument Version 2 (MAYSI-2) within 2 weeks of referral to the department. Individuals with a “caution” score are identified and immediately referred to a Psychiatrist for a full evaluation. If a child is in a detention center, they are placed under “constant watch” for observation. If not in a detention center (i.e., living at home in the community), they are triaged into a crisis intervention program operated by clinicians and supervised by a Psychiatrist. This information (suicide risk, referral to psychiatrist, program participation) is logged in the electronic record system. The same procedure is employed if a suicide risk is identified at any point during involvement with JJ.

Within 24 hours prior to the first session, the TCU research assistant (RA) will confirm with the TCJS Director of Research (DOR) that the youth has met eligibility requirements (one or more indicator of substance use; on community supervision; no indication of suicide risk or thought disorder). Biweekly, RAs will provide a list of active participants to the DOR, who will identify any youth with a newly identified risk for suicide or thought disorder. Study staff also will monitor and report disclosures of suicidal ideation during study meetings as required by law and in accordance with TCJS departmental procedures.

Plan for Monitoring Adverse Consequences

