Implementation feasibility measures will be recorded, summarized, and reviewed monthly by the PI and team in order to inform real-time protocol adjustments (e.g., changes in recruiting practices if target numbers are not reached). Once the targeted youth recruitment goal has been achieved, psychometric properties of baseline measures will be conducted (means, SD, coefficient alpha, exploratory/confirmatory factor analysis). Because the design calls for repeated measures at baseline, month 1, and month 3, measures will not be revised between administration points.

However, psychometrics (conducted on data from all time points) will be used to inform modifications prior to a full-scale R01 RCT and reliability of scales for use in exploratory analyses of intervention efficacy.

Baseline characteristics will be included as covariates in analyses. The distal outcome will be the percent of study subjects who use drugs (self-report, corroborated with positive urine test) at follow-up (1- and 3-months). All study participants (regardless of study retention) will be included in analyses (i.e., an intent-to-treat approach; ITT). Baseline variables that directly relate to our aims (e.g., drug use, risky sex practices) will be evaluated for use as covariates. Abstinence at each

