follow-up time point will be compared using chi square test. Our proximal outcomes will include putative measures (e.g., problem recognition, decision making, intention to reduce personal risk) and receipt of SU services (dichotomous measure from youth records). Because proportions of females and their SU rates are generally lower among JJ youth compared to males,⁶ and males/females may respond differently to MEC interventions,¹⁶ we will explore sex (as a biological variable) differences in SU, risky sex practices, and exploratory outcomes using univariate analyses (e.g., chi square, t-tests, ANOVA). We will also explore potential racial/ethnic disparities in order to more fully inform whether cultural modifications are needed for a subsequent application. A log rank test will be used to assess intervention dropout. Participants who withdraw consent or are lost to follow up will be missing on outcome measures. To address this, stochastic multiple-imputation will be attempted, which will provide maximum likelihood estimates, account for uncertainty in missing values, and provide unbiased estimates of the treatment effect if data are missing at random. Effect sizes will be used to calculate sample sizes needed for the larger R01. Calculations will include samples needed to assess intervention feasibility across sex and race/ethnicity subgroups.

21. Check List for the Items That Need to be Submitted:

a. Protocol	
b. Consent document	
c. HIPAA form if applicable	
d. Protecting Human Research Participants Training certificate for each investigator	
e. Recruitment flyers, letters, ads, etc.	
f. Questionnaires or other documents utilized in screening and data collection	

Principal Investigator Assurance

22. By signing below, I certify to the following:

- The project described herein will be conducted in accordance with applicable TCU policies and procedures, as determined by the IRB of record. All Human Subject Research projects occurring at TCU must be conducted in compliance with the Office of Human Protection ("OHRP") regulations at 45 CFR 46 and all other applicable federal and state laws and regulations (collectively "Applicable Law")
- I have a working knowledge of Applicable Law

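### The distal outcome is the percent using drugs at follow-up, which as defined does not measure the reduction in use named in the Summary

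*Combined protocol and SAP*

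**What the plan says.** - **Objective (Summary).** "Distal outcomes include reduction in risky behaviors, including substance use (self-report and urinalysis"; sexual health risk is listed alongside.
- **Entry (Section 12, Inclusion Criteria).** "Youth ages 14-18 on community supervision are eligible if they have 1 or more indicator(s) of substance use". The eligibility confirmation before the first session, in the data and safety monitoring plan (Section 16), repeats the criterion: "one or more indicator of substance use; on community supervision; no indication of suicide risk or thought disorder". Neither place defines an indicator, sets a look-back window or asks for current use.
- **Outcome (Section 20).** "The distal outcome will be the percent of study subjects who use drugs" at months 1 and 3, by self-report with a positive urine test as corroboration.
- **Analysis set and test (Section 20).** "All study participants (regardless of study retention) will be included in analyses". For abstinence, each "follow-up time point will be compared using chi square test". No second group, baseline pairing or model is named for that test.
- **Baseline data (Sections 15, 19 and 20).** Assessments are planned at baseline, month 1 and month 3. The measures stay unchanged between them, and records are linked by a research ID. Section 20 says baseline characteristics will be covariates, then says baseline drug use will be evaluated as one.
- **Design (Section 15).** Youth receive the four sessions, and no allocation or control arm is described. The adverse-event text in Section 16 refers to study groups and a comparison group, but no section says how these are formed.
- **Use of results (Section 20).** Effect sizes will set the sample size of the larger R01.

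**The concern.** The objective is a change, but the defined outcome is a level. A youth who was not using at entry and is not using at month 3 counts exactly as one who stopped. With no control arm described, baseline is the only reference available for this outcome, and neither the definition nor the named test uses it. Followed as written, the analysis reports a follow-up percentage that a reader cannot classify as a fall, no change or a rise.

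What is at stake is mainly the R01. A use or abstinence rate taken from this pilot mixes youth who could stop with youth who had nothing to stop, in a proportion that the plan does not ask to be reported.

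**Working it through.** **Inputs from the documents.** About 60 youth (Section 12); outcome, analysis set and test as in Section 20. There is no planned figure to reproduce: the documents give no use rate, effect size, alpha, power or dropout. Every rate below is an assumption, shown as a range where it drives the result.

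**Step 1: the same follow-up figure under different baselines.** Change in use = follow-up percent − baseline percent. For 40% using at month 3:
- baseline 100%: 40 − 100 = −60 points
- baseline 70%: 40 − 70 = −30 points
- baseline 40%: 40 − 40 = 0
- baseline 30%: 40 − 30 = +10 points

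The outcome as defined reads 40% in all four cases.

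**Step 2: dependence on baseline non-use.** Let f be the share not using at baseline and q the share of baseline users who stop, with no new use. Then follow-up abstinence = f + (1 − f)q, and the fall in the percent using = (1 − f)q.

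| f | abstinent at follow-up if q = 0 | abstinent at follow-up if q = 30% | fall in use if q = 30% |
|---|---|---|---|
| 0% | 0 of 60 | 30% | 30 points |
| 20% | 12 of 60 | 44% | 24 points |
| 40% | 24 of 60 | 58% | 18 points |
| 60% | 36 of 60 | 72% | 12 points |

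At a constant q, the reported abstinence rises with f while the actual fall in use shrinks. At f = 0 the two agree, so if nearly every youth uses at entry the difficulty is slight.

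**Step 3: movement in both directions.** Take 24 baseline non-users of whom 10% start, and 36 baseline users of whom 35% stop. Expected abstinent at follow-up = 24 × 0.90 + 36 × 0.35 = 21.6 + 12.6 = 34.2, and 34.2/60 = 57%. Alone, 57% says nothing about reduction. Beside the baseline abstinence of 24/60 = 40%, it shows a net fall in use of 17 points (60% to 43%).

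**Step 4: what a paired test would use.** With 36 of 60 using at baseline, suppose 11 stop and 3 start. Use falls from 36/60 = 60% to (36 − 11 + 3)/60 = 28/60 = 47%. The exact McNemar test depends only on the 14 youth who changed: p = 2 × P(X ≥ 11 | n = 14, 0.5) = 0.057. The follow-up percent alone contains none of this information.

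**Step 5: consequence for the R01.** Suppose a later two-arm trial with stopping rates of 20% and 50% among baseline users, baseline non-users staying abstinent, two-sided alpha 0.05 and 80% power. Per arm, n = [1.96√(2p̄(1 − p̄)) + 0.842√(p₁(1 − p₁) + p₂(1 − p₂))]² / (p₁ − p₂)².
- f = 0: 20% against 50%; (1.322 + 0.539)²/0.30² = 38.5, so 39 per arm.
- f = 40%: 0.4 + 0.6 × 0.2 = 52% against 0.4 + 0.6 × 0.5 = 70%; (1.352 + 0.571)²/0.18² = 114.1, so 115 per arm.

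The required size nearly triples with f, so the pilot needs to report f.

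**The case against.** A reader might infer that the study cannot show a reduction in use. The documents do not support that. Baseline is assessed with the same measures, records are linked within person, and baseline drug use is named as a candidate covariate. A model conditioning on baseline use would separate users from non-users. What stands is narrower: no such model is named for abstinence, and a chi-square test takes no covariates.

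A reader might also infer that many enrolled youth were not using at entry. Nothing establishes that. An indicator is left undefined; it could mostly reflect current use, and the assessment package and the state agency proposal are not in the text available here.

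Nor should the 57% in the mixed example be set against the 35% of baseline users who stopped. One is a prevalence and the other a stopping rate. New use offsetting stopping is no defect either: net prevalence in all participants is a legitimate intent-to-treat quantity.

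Restricting the outcome to baseline users is tempting but weak without a comparator, because it invites regression to the mean. If every youth independently had a 60% chance of use in any window, 40% of baseline users would appear to stop with no real change, while the all-participant figure would stay at 60%.

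The point that efficacy is exploratory in a feasibility pilot also stands. It limits the consequence, but Section 20 still carries the effect sizes forward to the R01. Without a comparator, even a well-measured change supplies no treatment effect.

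**Conclusion.** The concern holds as a mismatch between objective and outcome definition. The Summary names reduction; Section 20 defines follow-up prevalence and names a test that uses no baseline value. Entry does not require current use and no control arm is described, so the figure as defined does not distinguish a fall from no change or a rise.

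Its size rests on the share not using at baseline, which the documents do not give. Over an assumed 20% to 60%, between 12 and 36 of 60 youth would count as abstinent with no change at all; near 0% the distortion is negligible. The gap lies in the definition and the named analysis, not in the planned baseline assessment. It should be corrected before analysis, but it does not touch the feasibility and acceptability aims.

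**What to change.** In Section 20:

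1. Define the distal outcome as the within-person change in the percent of all participants using drugs, from baseline to month 1 and to month 3. Show the baseline percent beside each follow-up percent.
2. Replace the chi-square at each follow-up with a paired method: a McNemar test for each follow-up, or a repeated-measures logistic model over the three times.
3. Use one definition of use that is available at all three times: self-report, with urine results as corroboration where they exist. The documents do not describe urine collection at baseline, so a definition requiring it could need data that are not planned.
4. Report stopping among baseline users and new use among baseline non-users as descriptive secondary figures. Note that the first is open to regression to the mean, and that without a comparator no change can be attributed to the intervention.

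Eligibility, the intent-to-treat set and the assessment schedule stay as they are. The cost is a little more analysis, and wider intervals for the subgroup figures because each rests on only part of the 60 youth.
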